### 8.5.2 Analysis of Primary Endpoints

For the dose escalation parts the analysis will focus on the number of subjects experiencing a DLT. The SMC will receive results of a Bayesian 2-parameter logistic model with overdose control updated with the observed DLT data for SMCs dedicated to dose escalation decisions (1, 30). A separate model will be set up for monotherapy **CCI**

**CCI**

Recommendation on next dose of the model is based on a loss function (probabilities of being in 1 of the 4 toxicity probability intervals) will be multiplied with a loss term as follows:

$0 \times P(\text{target dosing } [0.17-0.35]) + 1 \times P(\text{for over } [0.35-0.67] \text{ or under dosing } [0-0.17]) + 2$

$\times P(\text{excessive dosing } [0.67-1]).$

In addition, only doses that have a corresponding probability of less than 25% that the true DLT rate is more than 35% (overdose control) are recommended by the model. The recommended dose level from the Bayesian model for the next cohort is the dose with the lowest loss function from all doses fulfilling the overdose control rule. This Bayesian escalation approach will be used to assist the SMC to select the next dose from a predicted set of acceptable doses (eg, 100, 200, 400, 600, 800 and 900 mg BID). The SMC may choose a different dose or dosing regimen than suggested by the Bayesian escalation approach.

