### Treatment Period:

The treatment period will begin at the first dose of M4112 in Cycle 1 Day 1 and consist of consecutive 28-day cycles of continuous M4112 (BID or other regimen determined by the SMC), either as monotherapy **CCCI**

Subjects will be instructed to take M4112 at least 1 h prior to a meal and at least 2 h after a meal. Meal times should be collected on the appropriate eCRF.

Eligible subjects will initiate therapy at the dose level appropriate at the time of enrollment. The Sponsor's Medical Responsible, or designee, must confirm enrollment and dose level (during dose escalation only) after receipt of the appropriate information relating to study entry.

Subjects who tolerate study treatment without significant clinically relevant toxicities may continue to receive their assigned dose as long as there is no evidence of confirmed disease progression.

Part IA to Part IC: Dose Escalation

A broad dose range in monotherapy is planned to be investigated to determine the safety profile, tolerability, PK, and PD markers and to explore signs of antitumor activity in subjects with advanced solid tumors.

Subjects will receive M4112 at the starting dose of 100 mg BID (100 mg BID which equals to 200 mg total daily dose) at least 1 h prior to a meal and at least 2 h after a meal. Cohorts will consist of 3 subjects each, if not decided differently by the SMC. Cohorts will consist of 3 subjects each, if not decided differently by the SMC. The first subject of each dose level will be observed for at least 5 days before the second subject can be treated. Subsequent subjects may receive first dosing at no less than 48 h intervals between subjects for the first 2 cohorts of mono

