**CCI** If the safety profile is acceptable and agreed by the SMC, the 48 h observation after Subject 2 may be removed. The safety and tolerability data and available PK and PD data (as minimum Day 1 and Day 15 PK and PD data from previous cohort and all available PK and PD data from the current cohort) will be reviewed by the SMC at the end of each cohort. In cases where enrollment of last subject in a dosing cohort was delayed, the SMC may decide (based on available data) upon enrollment and dose for the next dosing cohort before all subjects in a cohort have completed Cycle 1. The SMC will be assisted in their dosing and regimen (administration schedule) decisions by PK, PD, and a Bayesian 2-parameter logistic regression model modeling DLT rate with overdose control. The model incorporates nonclinical toxicity data in the prior and DLTs observed until the SMC meeting to provide a recommended dose for the next cohort. The SMC can choose a dose different from the one recommended by the model. During the dose escalation part of the study, the SMC will advise, primarily based on safety (DLTs) during the first cycle, and any TEAE observed in subsequent cycle that in the opinion of the SMC needs to be taken into account (additional DLT criteria, see Section 6.2.4), for the overall evaluation of the safety and proposal of dose escalation dose, dose de-escalation, dose level expansion or regimen change, or it may recommend suspension of enrollment, with the final adjudication being a Sponsor decision. A Bayesian 2-parameter logistic regression model will incorporate observed DLTs from all previously completed cohorts to provide a recommended dose for the next cohort. The SMC may also recommend a cohort size different from 3 subjects as the Bayesian design allows dose recommendation based on less or more than 3 subjects.

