Based on the absence of clinical signs or other adverse findings, the 30 mg/kg/day in the dog was considered the NOAEL in this study. The subsequent dose, 100 mg/kg/day, was considered not tolerated due to the adverse findings in an early sacrificed (Day 15) male dog administered 100 mg/kg/day. No HNSTD was defined in dogs in the 4-week toxicity study. The dose of 30 mg/kg/day was defined as the NOAEL and the starting dose in Phase I takes into consideration the HNSTD according to the guideline ICH S9 as well as margins relative to the NOAEL in the dog the most sensitive animal species (described further in Section 5.2.3) and translates to a human equivalent dose (HED) of approximately 16.7 mg/kg/day; the starting dose

is approximately 1/6 of the HED at 2.8 mg/kg/day or approximately 100 mg for a 70 kg human administered BID.

Prespecified ascending doses of 100, 200, 400, 600, 800, and 900 mg BID (means respectively, 100 mg BID for 200 mg total daily dose, 200 BID for 400 mg total daily dose, 400 mg BID for 800 mg total daily dose, 600 mg BID for 1,200 mg total daily dose, 800 BID for 1,600 mg total daily dose, 900 mg BID for 1,800 mg total daily dose) as single agent in 28-day cycles are foreseen. Dose escalation decisions will be driven primarily by DLT, safety, and tolerability. The MTD may not be reached in the anticipated PD active dose range of M4112, therefore, the assessment of PD effects may be used to explore the optimal biological dose (OBD) and to inform on the RP2D.

A BID dosing regimen will be followed based on PK modelling to achieve the target  $C_{min}$  over the dosing interval at a lower total daily dose and thereby reducing  $C_{max}$  and AUC over the day to potentially improve safety and tolerability when compared to QD dosing. Based on PK data from subjects, the SMC will evaluate whether this regimen should be continued or a different regimen explored.

CCI

CCI

In principle, dose escalation of single agent M4112 will proceed according to the recommendation of the SMC to the upper end of the above given dose range, unless the MTD has been reached or there is excess of PK nonlinearity, or the SMC recommends to end dose escalation following review of safety, tolerability, PK and PD results. Depending on the observed toxicity profile and available measured PK and PD, or dose regimen different or higher than the prespecified doses may be tested.

CCI

• CCI

• CCI

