## 8 Statistics

### 8.1 Sample Size

A Bayesian model is applied to assist the SMC in dosing recommendations. Bayesian models will be set up for IDO monotherapy and CCI [REDACTED] separately.

For this sample size assessment, it is assumed that it is not necessary to enroll additional subjects at RP2D or MTD and no additional levels are tested (see Section 5.1).

It is anticipated that 24 to 30 evaluable subjects (6 projected dose levels with 3 to 12 subjects each) may be needed in order to test the planned dose range of IDO monotherapy. As it is not anticipated that MTD occurs in the planned dose range, DLTs are not expected to occur frequently. Therefore, the following scenario could be anticipated, assuming 2 DLTs:

- For single agent escalation: 4 dose levels with 3 subjects each and 2 dose levels with 6 subjects each.

As inherent in dose escalation studies, the sample size cannot be prespecified. The SMC will recommend doses. Dose regimens are not prespecified as it is dependent on DLTs, PK, and PD observed.

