## Appendix V: Operating Characteristics of Bayesian Dose Escalation 2-Parameter Logistic Regression Model with Selected Prior and Overdose Control Boundary at 35%

The following table shows the operating characteristics of the Bayesian logistic regression dose escalation model. It shows potential scenarios for dose escalation and associated estimated posterior probabilities of estimated DLT probability being in one of the toxicity intervals.

				Prior Specifications: $E(\alpha)=-0.800119$ , $E(\beta)=0.464697$ , $Var(\alpha) = 1.5^2$ , $Var(\beta) = 1.5^2$ , $Cov(\alpha, \beta) = 0$						
				Recommended Dose Considering			Posterior Probability of DLT Probability of Recommended Dose (Model and Overdose Control) being in Toxicity Interval			
Scenario	Doses Tested	Dose-Limiting Toxicities/ Number of Subjects	Loss Function	Overdose Control	Model and Overdose Control	[0,0.17] “Under Dosing”	(0.17,0.35] “Target Dosing”	(0.35,0.67] “Over Dosing”	(0.67,1] “Excessive Dosing”	
1	100 mg	0/3	800 mg	600 mg	600 mg	0.67	0.19	0.12	0.02	
1a	100 mg	1/3	100 mg	100 mg	100 mg	0.43	0.32	0.22	0.02	
1b	100 mg	1/6	200 mg	200 mg	200 mg	0.49	0.36	0.15	<0.01	
2	100 mg 200 mg	0/3 0/3	800 mg	800 mg	800 mg	0.54	0.24	0.18	0.04	
2a	100 mg 200 mg	0/3 1/3	400 mg	200 mg	200 mg	0.59	0.31	0.10	<0.01	
2b	100 mg 200 mg	0/3 1/6	400 mg	400 mg	400 mg	0.48	0.37	0.15	<0.01	
3	100 mg 200 mg 400 mg	0/3 0/3 0/3	800 mg	800 mg	800 mg	0.61	0.23	0.14	0.02	
3a	100 mg 200 mg 400 mg	0/3 0/3 1/3	600 mg	400 mg	400 mg	0.60	0.31	0.09	<0.01	
3b	100 mg 200 mg	0/3 0/3	600 mg	600 mg	600 mg	0.48	0.36	0.15	<0.01	

				Prior Specifications: $E(\alpha)=-0.800119$ , $E(\beta)=0.464697$ , $Var(\alpha) = 1.5^2$ , $Var(\beta) = 1.5^2$ , $Cov(\alpha, \beta) = 0$						
				Recommended Dose Considering			Posterior Probability of DLT Probability of Recommended Dose (Model and Overdose Control) being in Toxicity Interval			
Scenario	Doses Tested	Dose-Limiting Toxicities/ Number of Subjects	Loss Function	Overdose Control	Model and Overdose Control	[0,0.17] "Under Dosing"	(0.17,0.35] "Target Dosing"	(0.35,0.67] "Over Dosing"	(0.67,1] "Excessive Dosing"	
	400 mg	1/6								
4	100 mg 200 mg 400 mg 600 mg	0/3 0/3 0/3 0/3	900 mg	800 mg	800 mg	0.70	0.20	0.09	<0.01	
4a	100 mg 200 mg 400 mg 600 mg	0/3 0/3 0/3 1/3	600 mg	600 mg	600 mg	0.57	0.33	0.10	<0.01	
4b	100 mg 200 mg 400 mg 600 mg	0/3 0/3 0/3 1/6	800 mg	800 mg	800 mg	0.42	0.36	0.21	0.02	

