#### Bayesian two-parameter logistic model

Upon completion of the DLT observation period of each cohort, summary statistics of the posterior probability distribution of the true DLT rate (2.5%, 25%, 50%, 75%, and 97.5% quantiles) for each predefined dose level will be updated and estimated according to the logistic model. Using data from all subjects completing the DLT period or experiencing a DLT during this period at the completion of a new cohort (and data from all previous cohorts: DE analysis set), the Bayesian logistic model provides a recommended dose level for the next cohort.

Recommendation is based on a loss function (probabilities of being in 1 of the 4 intervals will be multiplied with a loss term as follows:

$0 * P(\text{target dosing (estimated DLT rate in (0.17-0.35])}) + 1 * P(\text{for over dosing (estimated DLT rate in (0.35-0.67]) or under dosing (estimated DLT rate in [0-0.17])}) + 2 * P(\text{excessive dosing (estimated DLT rate in (0.67-1])})$ .

In addition, only doses with estimated probability of  $\leq 25\%$  that the true DLT rate is more than 35% (overdose control) will be recommended by the model. The recommended dose level resulting from the model for the next cohort is the dose with the lowest loss function from all doses fulfilling the overdose control rule. This Bayesian escalation approach will be used to assist the SMC to select the next dose from a predicted set of acceptable doses, i.e., 100 mg, 200 mg, 400 mg, 600 mg, 800 mg and 900 mg BID. It is possible to choose a dose(s) not within the pre-specified dose-escalation plan. Using a Bayesian model-based design aids the SMC in dosing decisions by providing more information compared to a 3+3 design (e.g., an estimated dose-toxicity curve with confidence information utilizing data on all subjects in DE analysis set at time of analysis).

The model will continue to be updated at each SMC until the SMC has decided to stop dose escalation.

Prior distribution and likelihood are used to calculate the posterior probabilities based on Bayes theorem.

The likelihood is defined based on a binomial distribution, modelling the rate of subjects with at least 1 DLT.

The prior distribution is set-up as follows:

The relationship between dose and toxicity rate is defined by

$$P(DLT|d_j, \alpha, \beta) = \frac{\exp\left(\alpha + \exp(\beta) * \log\left(\frac{d_j}{d_{ref}}\right)\right)}{1 + \exp\left(\alpha + \exp(\beta) * \log\left(\frac{d_j}{d_{ref}}\right)\right)}$$

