## Pre-defined doses
dose<-c(100,200,400,600,800,900)

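### The model's next-dose rule has no visible limit on skipping untested levels: Appendix V recommends 600 mg BID after 0/3 at 100 mg, where the prespecified sequence goes to 200 mg

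*Protocol*

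**What the plan says.** Protocol 8.5.2 scores each dose by a loss of 0 for target, 1 for under- or over-dosing and 2 for excessive dosing. It drops any dose with a 25% or greater posterior probability that the DLT rate exceeds 35%. The recommended dose "is the dose with the lowest loss function from all doses fulfilling the overdose control rule". The SMC analysis plan, section 16.1, has the same rule: "The recommended dose level resulting from the model for the next cohort is the dose with the lowest loss function". Its example code offers all six levels, "dose<-c(100,200,400,600,800,900", at every update.

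The planned escalation is level by level:

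- Protocol 5.1 fixes the start ("Subjects will receive M4112 at the starting dose of 100 mg BID") and lists "Prespecified ascending doses of 100, 200, 400, 600, 800, and 900 mg BID".
- Protocol 8.1 bases the sample size on "4 dose levels with 3 subjects each and 2 dose levels with 6 subjects each", so all six levels are used.
- Appendix V ("It shows potential scenarios for dose escalation and associated estimated posterior probabilities") tests the levels in order from row to row.

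The model is advisory. Protocol 5.1 states: "The SMC can choose a dose different from the one recommended by the model". The final decision is the Sponsor's.

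**The concern.** The rule chooses freely among all six levels. With few data and no DLTs, the lowest-loss dose lies near the top of the range, because the low doses carry a high probability of under-dosing. Overdose control is then the only brake in the model, and the prior is wide enough to let high levels through early. With no data at all, 600 mg already passes (probability 0.248 against the 25% limit) and is the model's choice. Three subjects without a DLT at 100 mg leave that choice unchanged.

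This is a first-in-human study. Protocol 5.1 sets the start at about one sixth of the human equivalent of the dog NOAEL (2.8 against 16.7 mg/kg/day, 70 kg person). By the same arithmetic, 600 mg BID is 1,200/70 = 17.1 mg/kg/day. The first recommendation therefore goes from one sixth of that equivalent to about the whole of it on the strength of three subjects. The planned sequence reaches 600 mg too, but only after cohorts at 200 and 400 mg. Those cohorts would also show the PK nonlinearity that the plan names as a reason to stop escalating.

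**Working it through.** **Inputs** (Protocol 8.5.2; SMC analysis plan 16.1)

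- logit P(DLT at dose d) = α + exp(β) × log(d/900).
- Independent normal priors: α with mean log(0.31/0.69) = −0.8001, β with mean log[(log(0.11/0.89) − log(0.31/0.69)) / log(400/900)] = 0.4647, variance 1.5² each.
- Levels 100, 200, 400, 600, 800 and 900 mg; cut-points 0.17, 0.35 and 0.67.
- Loss = P(under) + P(over) + 2 × P(excessive).
- Overdose control: P(DLT rate > 0.35) < 0.25. The SMC plan's ≤ 25% gives the same doses in scenarios 1 to 3.

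**Method.** Posterior by numerical integration over a grid of α and β (1401 × 1401, ±7 prior SD) with a binomial likelihood.

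**Reproducing Appendix V.** All 18 recommended doses match. For the three rows at issue, the interval probabilities (under / target / over / excessive) are:

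| Scenario | Data | Model's dose | Appendix V | Recomputed |
|---|---|---|---|---|
| 1 | 0/3 at 100 mg | 600 mg | 0.67 / 0.19 / 0.12 / 0.02 | 0.668 / 0.190 / 0.122 / 0.021 |
| 2 | 0/3 at 100 and 200 mg | 800 mg | 0.54 / 0.24 / 0.18 / 0.04 | 0.541 / 0.241 / 0.175 / 0.043 |
| 3 | 0/3 at 100, 200 and 400 mg | 800 mg | 0.61 / 0.23 / 0.14 / 0.02 | 0.609 / 0.229 / 0.137 / 0.024 |

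**Why the rule jumps.** Loss, with P(DLT rate > 0.35) in brackets:

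| Dose | Scenario 1 | Scenario 2 | Scenario 3 |
|---|---|---|---|
| 200 mg | 0.922 (0.027) | 0.960 (0.005) | 0.985 (0.001) |
| 400 mg | 0.870 (0.071) | 0.900 (0.029) | 0.946 (0.006) |
| 600 mg | 0.831 (0.142) | 0.839 (0.091) | 0.869 (0.041) |
| 800 mg | 0.812 (0.263) | 0.802 (0.218) | 0.796 (0.162) |
| 900 mg | 0.844 (0.380) | 0.832 (0.348) | 0.816 (0.307) |

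In scenario 1, 800 mg has the lowest loss but fails overdose control, so the recommendation falls to 600 mg. In scenarios 2 and 3, 800 mg has the lowest loss and passes.

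**Against the prespecified next level**

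| Scenario | Model's step | Planned step | P(DLT rate > 0.35), model | Same, planned | Ratio |
|---|---|---|---|---|---|
| 1 | 100 to 600 mg (6-fold) | 100 to 200 mg (2-fold) | 0.142 | 0.027 | 5.3 |
| 2 | 200 to 800 mg (4-fold) | 200 to 400 mg (2-fold) | 0.218 | 0.029 | 7.5 |
| 3 | 400 to 800 mg (2-fold) | 400 to 600 mg (1.5-fold) | 0.162 | 0.041 | 4.0 |

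**Effect of a cap.** Limiting candidates to at most one level above the highest tested changes rows 1, 2 and 3, to 200, 400 and 600 mg. The other 15 rows, including all 12 with a DLT, keep their dose.

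**Cost in subjects, no DLTs, cohorts of 3.** Uncapped, the model goes 100, 600, 800, 900 mg: 4 × 3 = 12 subjects. Capped, it goes through all six levels: 6 × 3 = 18. The Protocol 8.1 figure is 4 × 3 + 2 × 6 = 24, which adds two expansions.

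**The case against.** The strongest reply is that the model only advises. After 0/3 at 100 mg, 200 and 400 mg also pass overdose control. An SMC that picks 200 mg departs from the lowest-loss dose but stays within the acceptable set and within its stated powers. Text around 8.5.2 and 5.1 is redacted and the SMC charter is not available, so a limit on the SMC's step may exist. Other safeguards are in place: five days' observation of the first subject at each level, 48-hour spacing in the first two cohorts, and PK and PD review. All of this stands, and it is why the point concerns the advice and not a prediction of harm. It does not remove the point: the Appendix V column that combines model and overdose control prints 600, 800 and 800 mg, so no step limit acts on the recommendation.

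Four narrower objections also have force:

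- Rows 2 and 3 are not on the model's own path. They arise only if the SMC has already gone level by level.
- The row 3 step is two-fold, no larger than the plan's own early steps. Row 1 carries the argument, then row 2.
- In a monotone model a lower dose always has a lower overdose probability, so the ratios are partly built in. Posterior mean DLT rates at the model's doses are 0.156, 0.215 and 0.182, all below the 30% target.
- The SAP (February 2019) reports Part IA as completed and the study as terminated early, so a change now would serve only a later use of this design.

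**Conclusion.** The concern holds. As written and as tabulated in Appendix V, the model's rule has no visible limit on skipping untested levels. At the first three steps of a level-by-level escalation without DLTs, its advice contradicts the sponsor's own sequence, and the SMC has to set it aside to follow the plan. Overdose control binds in scenario 1 but does not hold the recommendation to the next level. At the next listed level, the probability of a DLT rate above 35% is about 4 to 8 times lower.

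This rests on the stated prior, loss and overdose limit, on cohorts of three, and on the readable text. It does not show that any subject would have been over-dosed. It is a cheap safety improvement that should be made.

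**What to change.** In Protocol 8.5.2 and section 16.1 of the SMC analysis plan, state that the model recommends the lowest-loss dose among levels that (a) pass overdose control and (b) are no higher than the next prespecified level above the highest level tested. Leave the SMC's right to choose another dose as it is. Restrict the candidate doses in the same way in the code and in whichever of the permitted packages is used to run or validate it. The example code sets an argument called constrain to FALSE. The documents do not define it, so its meaning should be confirmed before relying on it.

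Rerun Appendix V: rows 1, 2 and 3 become 200, 400 and 600 mg, in line with 5.1, 8.1 and the rows that follow.

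The cost is one sentence in each document, a small code change and the rerun. The downside is slower escalation if the drug is well tolerated: two more cohorts (18 − 12 = 6 subjects) on the path without DLTs, still within the 24 planned.

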**CCI**

**CCI**

If the SMC decides to change the dosing regimen, a separate model will be set up or the model extended to a partial order Continual Reassessment Method.

All subjects treated in dose escalation cohorts who miss  $> 5$  planned total daily doses of M4112 **CCI** in the first cycle (first 28 days) of the dose escalation part for other than safety reasons are not eligible for DLT assessment, will not be considered in the Bayesian model and will not formally be replaced. The SMC can still be adjourned and the Bayesian model will be updated with the data from the evaluable subjects.

The target probability for the MTD suggested by the model will be 30%. If the DLT probability of a potential MTD reaches sufficient precision, the SMC will be informed.

The 2-parameter logistic regression model will be set up as follows:

The relationship between dose and toxicity rate is defined by:

$$P(DLT|d_j, \alpha, \beta) = \frac{\exp\left(\alpha + \exp(\beta) * \log\left(\frac{d_j}{d_{ref}}\right)\right)}{1 + \exp\left(\alpha + \exp(\beta) * \log\left(\frac{d_j}{d_{ref}}\right)\right)}$$

Where  $d_j \in \{100 \text{ mg}, 200 \text{ mg}, 400 \text{ mg}, 600 \text{ mg}, 800 \text{ mg}, 900 \text{ mg}\}$  (BID dosing) and  $(\alpha, \beta)$  are bivariate normally distributed and the reference dose ( $d_{ref}$ ) is 900 mg.

The following parametrization is chosen for the monotherapy prior:

$$E(\alpha) = -0.8001$$

$$E(\beta) = 0.4647$$

$$\text{Var}(\alpha) = 1.5^2, \text{Var}(\beta) = 1.5^2, \text{Cov}(\alpha, \beta) = 0$$

This would correspond to:

Dose	100 mg	200 mg	400 mg	600 mg	800 mg	900 mg
Prior mean DLT rate	9%	12%	17%	22%	29%	36%
Prior median DLT rate	1%	3%	7%	13%	22%	30%

DLT = Dose-limiting toxicity.

For more information on operating characteristics of the prior, see [Appendix V](#).

Posterior distribution and the recommended next dose level will be calculated using R version 3.1.2 or higher with library package bcrm [\(38\)](#) or package CRMPack or EAST version 6.4 or higher.

At interim analysis, after end of dose escalation, and main analysis, the number and proportion of subjects experiencing DLTs will be reported by dose level, based on observations during the first treatment cycle. Posterior probabilities (2.5%, 25%, 50%, 75%, and 97.5% quantiles) will be estimated.

The Dose Escalation Analysis Set will be used for this analysis.

